5.6 Concomitant Medications

Consistent with subject safety and comfort, administration of any prescription or over-the-counter drug products other than study medication should be minimized during the study period. Subjects should be discouraged from use of street drugs, herbal remedies, self-prescribed drugs, tobacco products, or excessive alcohol during the clinical study.

If considered necessary for the subject’s wellbeing, drugs for concomitant medical conditions or for symptom management may be given at the discretion of the investigator. The investigator’s decision to authorize the use of any drug other than study drug should take into account subject safety, the medical need, the potential for drug interactions, the possibility for masking symptoms of a more significant underlying event, and whether use of the drug will compromise the outcome or integrity of the study.

Subjects should be instructed about the importance of the need to inform the clinic staff of the use of any drugs or remedies (whether prescribed, over-the-counter, or illicit) before and during the course of the study.

Recommendations with regard to specific types of concomitant therapies, supportive care; diet and other interventions are as follows:

Concomitant medications are recommended as prophylaxis for nausea, vomiting, and infections, and are allowed for managing myelosuppression as shown in Table 3. Myelosuppression is expected in patients with AML due to underlying disease, as well as due to chemotherapy (such as 5-azacytidine), or both. Most patients have neutropenia, thrombocytopenia, or both at study entry. Significant or life-threatening myelosuppression may be managed with growth factor support and blood transfusion according to institutional standard of care, American Society of Clinical Oncology (ASCO) Practice Guidelines, and/or NCCN Practice Guidelines.

Infections secondary to myelosuppression are common in patients with AML, and may be related to underlying disease, chemotherapy, or both. Therefore, the use of prophylactic antibiotics, antifungal agents, and antiviral agents is recommended according to institutional standards.

Since the effect of both avelumab and 5-azacytidine may be delayed, patients with high WBC counts may receive hydroxyurea prior to study entry. Hydroxyurea is allowed before the start of study therapy and during the study treatment. Hydroxyurea use would be recorded in the case report form (CRF). Concurrent therapy for CNS prophylaxis or continuation of therapy for controlled CNS disease is permitted. With the exception of these agents, concomitant systemic chemotherapy or radiation therapy is not permitted. Subjects are not allowed to participate concurrently in any other therapeutic clinical study.

Subjects may be receiving systemic corticosteroids (daily doses ≤ 10 mg of prednisone or equivalent if indicated for adrenal replacement or antiemetic therapy), topical, or inhaled corticosteroids at study enrollment. They may receive systemic, topical, inhaled, or enteric corticosteroids while on study without limitation if they develop conditions that require corticosteroid therapy; such subjects are not required to discontinue study participation.

All ongoing medications and therapies (including herbal products, nutritional supplements, and nontraditional medications) at screening will be considered prior medications. Concomitant medication data will not be collected or entered into the case report form other than hydroxyurea as mentioned above; however, the subject's medication record will contain a list of concomitant medications. If a prohibited medication is inadvertently administered/ taken by the patient, the patient may remain on study as long as the prohibited medication is discontinued as soon as feasible. If a prohibited medication is considered essential for the patient well being, continuation on study with concomitant administration of such medication(s) will need to be discussed with and approved by the principal investigator and medical monitor

Table 4: Instructions for the use of concomitant medications and therapies

Category of Use	Medication	Comment on Use	Restriction on Use
Recommended	Prophylactic antibiotics, antifungal agents, and antiviral agents	Strongly encouraged	None
	Antiemetic agents	According to standard of care at MDACC	None
Allowed	Oral allopurinol or rasburicase	At investigators discretion	None
	Leukapheresis	According to standard of care at MDACC	Before induction 1 day 1 only
	Red blood cell	None	None

Category of Use	Medication	Comment on Use	Restriction on Use
	transfusion		
	Platelet transfusion	None	None
	White blood cell transfusion	At investigators discretion according to standard of care at MDACC	None
	Myeloid growth factors or platelet growth factor	At investigators discretion according to standard of care at MDACC	None
	Erythropoietin or darbepoetin	At investigators discretion according to standard of care at MDACC	None
	Any other medication for supportive care	At investigators discretion according to standard of care at MDACC	None

6.0 STUDY MEDICATIONS

6.1 **Avelumab (Anti-PD1)**

Avelumab is a fully human, monoclonal antibody of the IgG1 isotype that specifically targets and blocks the ligand (PD-L1) for PD-1 and has a preserved Fc domain. Avelumab is a sterile solution intended for intravenous (IV) infusion. Avelumab will be available as a sterile, clear, colorless, and non-pyrogenic solution for intravenous infusion. Each single-use vial contains 200 mg of avelumab, formulated as a 20 mg/mL preservative free acetated buffered solution at pH 5.2 in presence of Polysorbate 20 and Mannitol. It will supplied in Type I glass vials filled with 10 mL of liquid (200mg/vial), closed with a rubber septum and sealed with an aluminium flip off seal. The vials are not subject specific although there will be specific vial assignments by subject distributed by the Pharmacy in order to track drug usage and re-supply.

6.1.1 **Dose Calculation of Avelumab**

The determined dose is based on the patients bodyweight at each visit.

of assigned vials for a patient = (Current weight x dose level)/ 200 (mg/vial)

For example, a subject weighing 70 kg who is scheduled receive a dose of 10 mg/kg would require $700 \text{ mg} / 200 \text{ (mg/vial)} = 3.5$ vials i.e. 4 vials have to be used for this patient.

6.1.2 Preparation and Dispensing of Avelumab

The product storage manager should ensure that the study drug is stored in accordance with the environmental conditions (temperature, light, and humidity) as determined by the Investigator Brochure for avelumab (Appendix C). If concerns regarding the quality or appearance of the study drug arise, do not dispense the study drug and contact the supporting company (Pfizer) immediately. To prepare the dilutions, subsequent preparation steps must be accomplished by adequate trained personnel to guarantee the sterility of the product to be injected. Preferred method is to prepare the solution under laminar flow box using aseptic techniques.

Investigational product documentation must be maintained that includes all processes required to ensure drug is accurately administered. This includes documentation of drug storage, administration and, as applicable, storage temperatures, reconstitution, and use of required processes (e.g. required diluents, administration sets).

Avelumab vials must be stored in the original packaging at a refrigerated conditions 2°C to 8°C until use with a temperature log maintained daily and should be protected from light. Avelumab stored at room temperature 15-25°C or higher temperatures for extended periods of time might be subject to degradation. Avelumab must not be frozen. Recommended safety measures for preparation and handling of avelumab include laboratory coats and gloves.

For details on prepared drug storage and use time of avelumab under room temperature/light and refrigeration, please refer to the Avelumab Investigator Brochure section (Appendix C) for “Recommended Storage and Use Conditions”. Care must be taken to assure sterility of the prepared solution, as the product does not contain any anti-microbial preservative or bacteriostatic agent. No incompatibilities between avelumab and polyolefin bags have been observed.

6.1.3 Administration of avelumab

Patients will receive avelumab as an approximately 60 minute (+/- 30 minutes) IV infusion on Day 1 and day 14 (+/-3 days) of a treatment cycle every 28 days for 4 cycles or until CR (whichever occurs earlier) followed by a maintenance regimen (one dose of avelumab on day 1 of each cycle of 5-azacytidine). Dosing calculations should be based on the body weight assessed at the start of each cycle as described above. All doses should be rounded to the nearest milligram. The screening body weight may be used for dosing of cycle 1.

Prior to the preparation of dilution for final infusion, allow each vial to equilibrate to room temperature (15-25 C) preferably for 30-50 minutes. Rough shaking of the

solution must be avoided. The administration must be performed by adequately trained personnel. For application in clinical trials, avelumab must be diluted with a saline solution (Sodium Chloride for injection). The prepared avelumab dilution for infusion is connected to the infusion set equipped with a PES-inline filter and a 22G IV standard catheter. Alternatively, a permanent venous catheter or implantable PORT may be used. Prior to infusion the assembly is primed with the diluent. The administration is to be conducted in approximately 60 minutes by IV infusion. A constant infusion rate is achieved by using a microprocessor-controlled infusion pump. Variations in infusion times due to minor differences in IV bag overfill/under fill and institutional procedure on flushing chemotherapy lines will not result in protocol deviation. All infusion times are considered approximate. It is recommended (not mandatory) that immediately following the infusion of avelumab, using the same tubing, 25-100 mL normal saline are flushed and infused at the same rate to clear the infusion set of residual drug.

6.1.4 Patient Monitoring During Infusion

During the first infusion patient vital signs should be monitored prior to dosing, approximately 15 minutes after initiation of the infusion (then approximately every 15-20 minutes as indicated), at approximately 60 and 120 minutes after completion of the infusion, or longer if indicated, until the vital signs normalize or return to baseline. For subsequent infusions, vital signs should be collected prior to dosing, approximately every 30 minutes during dosing, and approximately 1 hour post dosing. There is a +/- 30-minute window allowed for all time points that vital signs are to be monitored.

6.1.5 Treatment of avelumab Related Infusion Reactions

Since avelumab contains only human immunoglobulin protein sequences, it is unlikely to be immunogenic and induce infusion or hypersensitivity reactions. However, if such a reaction were to occur, it might manifest with fever, chills, rigors, headache, rash, pruritus, arthralgia's, hypo- or hypertension, bronchospasm, or other symptoms. All Grade 3 or 4 infusion reactions should be reported within 5 days to the Pfizer Medical Monitor and reported as an SAE if criteria are met. Infusion reactions should be graded according to NCI CTCAE (version 4.03) guidelines.

Treatment recommendations for avelumab related infusion reactions, including severe hypersensitivity reactions and tumor lysis syndrome (TLS) are provided below and may be modified based on MD Anderson treatment standards and guidelines, as appropriate:

A. Avelumab Infusion Related Reactions

Symptoms

- Fever
- Chills
- Rigors

- Diaphoresis
- Headache

Management

Table 5. Treatment Modification for Symptoms of Infusion-Related Reactions

NCI-CTCAE Grade	Treatment Modification for Study Drug

Grade 1 – mild Mild transient reaction; infusion interruption not indicated; intervention not indicated.
	
Decrease the study drug infusion rate by 50% and monitor closely for any worsening. The total infusion time for study drug should not exceed 120 minutes.

Grade 2 – moderate Therapy or infusion interruption indicated but responds promptly to symptomatic treatment (for example, antihistamines, NSAIDs, narcotics, IV fluids); prophylactic medications indicated for ≤ 24 h.
	
Stop study drug infusion. Resume infusion at 50% of previous rate once infusion-related reaction has resolved or decreased to at least Grade 1 in severity, and monitor closely for any worsening.

Grade 3 or Grade 4 – severe or life-threatening Grade 3: Prolonged (for example, not rapidly responsive to symptomatic medication and/or brief interruption of infusion); recurrence of symptoms following initial improvement; hospitalization indicated for clinical sequelae. Grade 4: Life-threatening consequences; urgent intervention indicated.
	
Stop the study drug infusion immediately and disconnect infusion tubing from the subject. Subjects have to be withdrawn immediately from study drug treatment and must not receive any further study drug treatment.

IV = intravenous; NCI-CTCAE = National Cancer Institute-Common Terminology Criteria for Adverse Event; NSAIDs = nonsteroidal anti-inflammatory drugs.

Once the avelumab infusion rate has been decreased by 50% or interrupted due to an infusion-related reaction, it must remain decreased for all subsequent infusions. If the subject has a second infusion-related reaction Grade ≥ 2 on the slower infusion rate, the event will be reviewed by and discussed with the PI, and if felt to be in the best interest of the pt, and the pt is receiving benefit, the pt may continue on study and receive avelumab at the 50% lower infusion rate for all subsequent cycles.

If a subject experiences a Grade 3 or 4 infusion-related reaction at any time, the subject must discontinue study drug.

B. Severe Hypersensitivity Reactions and Flu-Like Symptoms

[figure not shown]
If hypersensitivity reaction occurs, the subject must be treated according to the best available medical practice. Subjects should be instructed to report any delayed reactions to the Investigator immediately.

For prophylaxis of flu-like symptoms, 25 mg of indomethacin or comparable nonsteroidal anti-inflammatory drug (NSAID) dose (for example, ibuprofen 600 mg, naproxen sodium 500 mg) may be administered 2 hours before and 8 hours after the start of each dose of avelumab IV infusion. Alternative treatments for fever (for example, paracetamol) may be given to subjects at the discretion of the Investigator.

C. Tumor Lysis Syndrome

In addition, since avelumab can induce antibody-dependent cell-mediated cytotoxicity, there is a potential risk of tumor lysis syndrome. Should this occur, subjects should be treated per the local guidelines and the management algorithm below ([Howard 2011](#)).

Assessment and Initial Management of Tumor Lysis Syndrome

TLS = tumor lysis syndrome

For further details regarding dose-calculation of avelumab, preparation and dispensing of avelumab, administration of avelumab, patient monitoring during infusion and treatment of avelumab related infusion reactions please see the Avelumab dosing procedure manual (Appendix H).

6.2 Azacytidine:

5-azacytidine will be commercially obtained. Refer to azacytidine prescribing information (appendix D) in addition to institutional standards for preparation and administration azacytidine.

6.3 Variations in infusion times of avelumab or 5-azacytidine due to minor differences in IV bag overfill/under fill and institutional procedure on flushing chemotherapy lines will not result in protocol deviation. All infusion times are considered approximate.

6.4 Unused or expired avelumab and 5-azacytidine will be safely disposed according to MD Anderson pharmacy standard guidelines.

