10.5 Investigator Communications with Pfizer

All Serious Adverse Events must be reported to Pfizer Clinical Trial Department

- All SAEs, whether related or unrelated to avelumab and all pregnancies must be reported to Pfizer (by the investigator or designee) within 24 hours.
- All SAEs should be reported via confirmed facsimile (fax) transmission, or scanned and reported via electronic mail to:
- **SAEs may be submitted directly via email.**

SAE Email Address: [contact]

SAE [contact]

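### Section 6.1.5 gives opposite outcomes, continue after PI review or stop avelumab, for a second infusion reaction of Grade 3 or 4 at the reduced rate

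*Combined protocol and SAP*

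**What the plan says.** **Second reaction.** The text after Table 5 in section 6.1.5 keeps a lowered infusion rate in force for later infusions. It then sets the trigger for review: "If the subject has a second infusion-related reaction Grade ≥ 2 on the slower infusion rate". The event goes to the PI, and subject to the patient's interest and benefit, "the pt may continue on study and receive avelumab at the 50% lower infusion rate for all subsequent cycles".

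**Grade 3 or 4 reaction.** The following paragraph reads: "If a subject experiences a Grade 3 or 4 infusion-related reaction at any time, the subject must discontinue study drug". The Grade 3/4 row of Table 5 says the same: "Subjects have to be withdrawn immediately from study drug treatment and must not receive any further study drug treatment".

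**Section 5.3.4.** The general avelumab discontinuation rules stop the drug at the second occurrence of the same Grade 2 event. They send infusion reactions of Grades 1 to 4 to their own guidance, so 6.1.5 is the operative text.

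**Infusion time.** Section 6.1.3 states: "Patients will receive avelumab as an approximately 60 minute (+/- 30 minutes) IV infusion". Table 5 halves the rate for Grade 1 and, after a stop, for Grade 2. A limit appears in the Grade 1 row only: "The total infusion time for study drug should not exceed 120 minutes".

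**Reporting.** Section 6.1.5 says "All Grade 3 or 4 infusion reactions should be reported within 5 days to the Pfizer Medical Monitor", and the same sentence goes on to require SAE reporting for events that qualify. Section 10.5 says that all SAEs "must be reported to Pfizer (by the investigator or designee) within 24 hours".

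**The concern.** The continuation sentence and the stopping paragraph stand next to each other, cover overlapping grades and point in opposite directions. The subject is re-exposure after a severe reaction to a drug whose infusion reactions section 2.1.6 lists among its important risks. Two investigators following the protocol in good faith could treat the same event differently. One patient would go on receiving avelumab and the other would not, and neither decision would clearly be a deviation. Later exposure, and the safety data that come from it, would depend on which sentence was applied.

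The infusion-time limit and the reporting deadlines sit in or near the same section and also fit together imperfectly. They are secondary, because neither decides whether a patient stays on avelumab.

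**Working it through.** **1. Continue or stop.** The rules for a second reaction at the reduced rate, grade by grade:

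| Grade of second reaction | Second-reaction sentence, 6.1.5 | Grade 3/4 paragraph and Table 5 row | Result |
|---|---|---|---|
| 1 | Does not apply (trigger starts at Grade 2) | Does not apply | No conflict |
| 2 | May continue after PI review | Does not apply | No conflict |
| 3 | May continue after PI review | Must stop | Opposite outcomes |
| 4 | May continue after PI review | Must stop | Opposite outcomes |

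Three places might settle Grades 3 and 4:

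- *Cross-reference or precedence within 6.1.5.* None is stated.
- *Section 5.3.4.* It hands infusion reactions back to their own guidance, so it adds no third rule and does not break the tie. The same hand-over largely removes any conflict with its repeat-Grade-2 rule.
- *Opening of 6.1.5.* It describes what follows as recommendations that may be adapted to institutional standards, whereas the Grade 3/4 rules are in mandatory terms. That does not say which rule prevails.

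**2. Infusion time (minor).** Inputs are a window of 60 ± 30 minutes (6.1.3), a 50% rate cut and a 120-minute limit (Table 5, Grade 1 row). For planned time T, a full infusion at half rate takes T / 0.5.

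- T = 60: 60 / 0.5 = 120 minutes. This reproduces the stated limit exactly.
- T = 30: 30 / 0.5 = 60 minutes, within the limit.
- T = 90: 90 / 0.5 = 180 minutes, which is 60 minutes over.
- Longest planned time that meets the limit for a full half-rate infusion: 120 × 0.5 = 60 minutes.

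For the infusion in which the reaction occurs, with the rate halved at minute t and ignoring any pause, total time is t + (T − t) / 0.5 = 2T − t. With T = 90 this is 180 − t. It meets the limit if t is 60 or more (180 − 60 = 120) and misses it if t is smaller (t = 30 gives 150).

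**3. Reporting (minor).** For a Grade 3 or 4 reaction that is not an SAE, only the 5-day line (5 × 24 = 120 hours) applies. For one that is also an SAE, the 24-hour line applies as well. The 6.1.5 sentence itself requires SAE reporting, so the two lines can run together. What is missing is any mention of 24 hours at that point.

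**The case against.** The strongest reply is that the documents already imply the answer. The continuation sentence is permissive and conditional; the stopping paragraph is mandatory, applies at any time and is repeated in Table 5. On that reading the mandatory rule limits the permissive one, which is left to cover second Grade 2 reactions. This is a reasonable way to read the section, and it narrows the defect to one sentence. It does not remove the defect. The continuation sentence is the more specific of the two (second reaction, slower rate) and can equally be read as an exception, and the text does not choose between the readings.

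A reader might also infer several stronger points that the documents do not support:

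- *That infusion time and reporting time also decide whether avelumab continues.* They do not; only the second-reaction rule does.
- *That no infusion planned above 60 minutes can be halved within the limit.* This holds for a full infusion at half rate, but not for a 90-minute infusion halved at minute 60 or later. The limit is also stated for Grade 1 only, and section 6.3 calls all infusion times approximate.
- *That later half-rate infusions necessarily breach the 30 to 90 minute window.* A base time of up to 45 minutes stays inside it (45 / 0.5 = 90). For longer ones, 6.1.5 expressly requires the slower rate, as a specific rule over a general one.
- *That a second reaction forces a 240-minute infusion.* That figure (60 / 0.25) assumes a second halving. The wording can equally mean keeping the first reduction, which gives 120 minutes.
- *That the same Grade 4 event has two competing deadlines.* The 5-day sentence adds SAE reporting, so a serious reaction follows both tracks.

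**Conclusion.** The point stands for one case. A second infusion reaction of Grade 3 or 4 at the reduced rate falls under two rules in section 6.1.5 with opposite outcomes and no stated precedence. Because it concerns stopping a study drug after a severe reaction, it should be resolved even though the case is narrow.

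Its frequency cannot be estimated, because the documents give no rate of second reactions at the slower rate. The conclusion assumes that Appendix H, the avelumab dosing manual to which the section refers for further detail and which was not available, does not settle the matter.

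The other two items are drafting notes. The 120-minute limit agrees with the nominal infusion, and a full half-rate infusion exceeds it only when the planned time is above 60 minutes, by up to 60 minutes at the edge of the window. The 5-day line lacks a cross-reference.

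**What to change.** The sponsor's clinical team should reconcile the second-reaction sentence in 6.1.5 with the paragraph after it and the Grade 3/4 row of Table 5, so that each grade of a second reaction has one stated outcome. Which outcome applies is a clinical decision on which no view is given here. Appendix H should be checked for consistency with the result.

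Two smaller edits can be made at the same time:

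- Reconcile the 120-minute limit with the ± 30 minute window, so that it is clear what applies to a half-rate infusion planned for more than 60 minutes.
- Add to the 5-day sentence a cross-reference to the 24-hour SAE deadline in section 10.5.

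The cost is a wording amendment. Sample size, monitoring boundaries and planned analyses are unchanged.
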